### **Randomization**

We will use a random number generator to randomize 10-14 Active Clinics to the Full Support Arm and 10-14 Active Clinics to the Self-Guided Arm. Randomization will be stratified (and balanced within strata) by CDRN and by participation (or not) in BP HOME, a concurrently running individual-level RCT that will provide home blood pressure monitoring devices to participating patients with a high blood pressure reading in clinic. As this is a real-world intervention that clinics will have to implement, they will not be blinded to the randomization.

### **Outcomes and measurements**

[figure not shown]
We will measure all outcomes by running a series of queries against EHR data maintained in the PCORnet Common Data Model. The outcomes will use individual patient-level data, reported in aggregate, for each participating clinic. Individual patients will not be followed over time across different repeat queries. Metrics are calculated for a specified 12-month measurement period, which allows time-dependent criteria, usually for including patients in the denominator (e.g., at least 1 visit during the measurement period, a diagnosis of hypertension at least 6 months ago, etc), and also “most recent” type criteria that can be used in metric definitions, usually for including patients in the numerator (e.g., BP is considered controlled depending on the most recent blood pressure measurement at an ambulatory visit within 6 months).

For the Intervention Clinics in Arms 1 and 2, all measurements will be obtained on a monthly basis for the purpose of guiding implementation of the intervention, with the 12-month measurement periods set to end at the end of each month. The primary outcome will compare the metrics obtained at baseline, defined as the measurement period that ends at the end of the month prior to initiation of the intervention, and at “6 months” (and at 12 and 18 months in secondary analyses) for each clinic, defined

as the measurement period that ends and fully includes the 6th full month (or 12th/18th month) after initiation of the intervention. So, for example, if the intervention launches on June 15, 2019, the baseline measurement period would be June 1, 2018 – May 31, 2019, and the 6-month measurement period used for the difference in differences calculation of the primary outcome would be Jan 1, 2019– Dec 31, 2019 (note that this is 7 months offset from the baseline measurement period).

For the Usual Care clinics, all measurements will be obtained on a quarterly basis through the BP Track surveillance project (a companion study), with measurement periods set to end at the end of each calendar quarter (Mar 31, June 30, Sept 30, Dec 31). The primary outcome will compare the metrics obtained at baseline, defined as the measurement period ending June 30, 2019 for all Usual Care sites, and at 6 months, defined as the measurement period ending Dec 31, 2019, for all Usual Care sites. These fixed dates were set under the assumption that the BP MAP intervention clinics will all launch their interventions within the window of May 15, 2019-August 31, 2019, and that this is therefore the most appropriate single 6-month comparison period, acknowledging that it will not correspond precisely to the same calendar time period as all of the intervention clinics (which will launch at different times), and that the measurement periods will be offset by 6 months vs. 7 months for the intervention clinics due to practical constraints.

For added clarity, these measurement periods are illustrated in the Figure below, with an arrow indicating an example launch date of June 15, 2019 for an Intervention Clinic.

Below we list the outcome measures of interest. Additional technical details for how the queries were constructed for each measure are provided in the supplemental materials.

- 1) Change in % BP Control at 6 months (primary outcome). Our primary outcome will be clinic-level change in the proportion of patients with controlled BP from baseline to 6 months after the start of the intervention. We define BP control according to NQF 0018 as the percent of eligible patients (defined above) with SBP <140 mmHg and DBP < 90 mmHg, based on measurements obtained at the most recent ambulatory clinical encounter at baseline (using the lowest measures of SBP and DBP at that encounter) and similarly at the 6-month time point after initiation of the intervention.

Secondary outcomes will include nine additional EHR-derived clinic-level metrics relevant to BP control. These metrics include alternate measures and BP control and improvement, as well as process and proxy measures aligned to the domains of the M.A.P. program including: indicators of BP measurement accuracy, medication intensification, average SBP reduction after medication intensification, and repeat visit within 4 weeks after a visit with uncontrolled HTN. Each metric below (and the primary outcome) will be measured as a change from baseline to 6 months (our primary time point), and change from baseline to 12 and 18 months. We will assess each metric overall (in all eligible patients) and within subgroups defined in Table 3.

- 2) BP Control to 2017 Guideline Goal, %. This alternative overall measure of BP control is identical to Metric 1, except that attainment of BP Control is defined by lower thresholds for blood pressure (SBP < 130 mmHg and DBP < 80 mmHg), as per the goal stated in the 2017 ACC/AHA Hypertension Guideline.
- 3) Improvement in blood Pressure, %. This overall measure of BP improvement defines BP improvement as either a reduction of 10 mmHg in SBP or achievement of SBP that is “adequately controlled” (SBP < 140 mmHg) over a period of 3 months, among hypertensive patients not previously controlled.
- 4) Confirmatory repeated blood pressure measurement, %. This process measure is designed to capture the practice of repeating a blood pressure measurement in the same visit when the first measurement done in clinic is high (SBP>140 mmHg or DBP>90 mmHg).
- 5) Medication intensification, %. This process measure captures the proportion of visits where BP is uncontrolled where a medication is ordered that is of a different class of medications than had previously been used. Note that this explicitly does not give credit for ordering a simple refill or medication dose increase, or use of a different medication in the same class.
- 6) Repeat visit in 4 weeks after uncontrolled HTN, %. This process measure captures the proportion of persons who had uncontrolled HTN who made a subsequent outpatient visit within the following 4 weeks.
- 7) Average SBP reduction after medication intensification, mmHg defined as the change in SBP observed between a visit with a medication intensification to the subsequent visit.
- 8) Terminal digit = zero, %. Inappropriate rounding of blood pressure measurements (usually to zero) leads to measurement error and worse treatment decisions. This metric is designed to catch this

behavior, which would lead to a terminal digit of zero of greater than 10% (if using an automated BP monitor is used) or greater than 20% (if a manual BP monitor is used with recommended rounding to even digits).

9) Use of fixed dose combination medications among patients taking 2 or more classes of medications, %. Use of fixed dose combination medications helps with adherence, promotes rational combinations of medications, and increases likelihood of achieving BP control.

10) Use of a CCB or thiazide-type diuretic among African-American patients on one medication %.

Calcium channel blockers (CCB) and thiazide-type diuretics are medication classes recommended to treat black or African American patients as first line monotherapy due to increased efficacy.

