**Table 3. Subgroups for HTE analysis**

Age: 18-44 vs. 45-64 vs. 65+

Race/ethnicity: NH White vs. NH Black vs. NH Asian vs. Hispanic (any race) vs. Other
Sex: Male vs. Female
Enrolling CDRN
HTE – Heterogeneity of treatment effects
NH – Non-Hispanic

**Exploratory Mediation analysis:** As many of our secondary outcomes are presumably process measures in the causal pathway to achieving BP control, we will perform a mediation analysis to understand the degree to which the potential added benefit of the Full Support intervention on BP control is explained by changes in the process measures. We will perform a mediation analysis using nested linear regression models for the effect of randomization assignment (i.e. Full Support vs. Self-Guided) on clinic level pre-post differences in percent control, first omitting, then adding each of our proposed mediators to the base model. The hypothesized process mediators will include pre-post changes in BP measurement accuracy, medication intensification, and average SBP reduction after medication intensification, and repeat visit in 4 weeks after uncontrolled HTN. These analyses will be implemented using the Paramed module in Stata statistical software  to calculate natural direct effect (NDE) of full-support on BP control and the natural indirect effect (NIE) through each mediator. The total causal effect (TCE) is the sum of the NDE and NIE. Dividing each NIE by the TCE will calculate the proportion of the causal effect explained by each mediator.

**Additional exploratory analyses:** We will explore temporal patterns in the effect of randomization assignment using linear mixed models for repeated clinic-level changes since baseline in primary and secondary outcomes assessed at 6, 12, and 18 months. These models will include random effects for clinic, as well as fixed effects for treatment assignment (as a categorical variable), and their interaction. Heterogeneity of treatment effects across time will be tested using a 2 degree-of-freedom chi-square test; in addition, a chi-square test for linear trend will be obtained by comparing the fitted treatment assignment effects at 6 and 18 months.

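### If visits are pooled, as the text most naturally reads, 41–50% of the 6-month window for process Metrics 4, 5, 7 and 8 is pre-launch, so an effect reads low at 6 months and appears to grow by 12 months

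*Combined protocol and SAP*

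**What the plan says.** Outcomes and measurements (combined protocol and SAP, III. Methods) sets one rule for all metrics: "Metrics are calculated for a specified 12-month measurement period, which allows time-dependent criteria". Baseline is "defined as the measurement period that ends at the end of the month prior to initiation of the intervention". The 6-, 12- and 18-month values come from "the measurement period that ends and fully includes the" sixth, twelfth or eighteenth full month after launch.

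The plan works an example: "if the intervention launches on June 15, 2019, the baseline measurement period would be" June 1, 2018 to May 31, 2019, and "the 6-month measurement period used for the difference in differences calculation of the primary outcome would be Jan 1, 2019" through Dec 31, 2019. It adds: "note that this is 7 months offset from the baseline measurement period". Launches are assumed to fall between May 15 and Aug 31, 2019.

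Every secondary metric is a change from baseline to 6 months, named as the primary time point, and to 12 and 18 months. The units differ:

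- Metric 5 is explicitly per visit: "This process measure captures the proportion of visits where BP is uncontrolled where a medication is ordered".
- Metric 4 (confirmatory repeat reading) is an event within a visit.
- Metric 7 (SBP change after intensification) is a pair of visits.
- Metric 8 (terminal digit zero) concerns readings; its denominator is not spelled out.
- Metric 6 (return within 4 weeks) is a proportion of persons.

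Additional exploratory analyses then models "repeated clinic-level changes since baseline in primary and secondary outcomes assessed at 6, 12, and 18 months", with a 2-df test of heterogeneity over time and a trend test comparing 6 with 18 months. Sensitivity analyses also describes mixed models of monthly changes over months 1 to 6.

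**The concern.** A 12-month window that closes about six months after launch must reach back before launch. A metric that uses only the latest reading is partly shielded from this. A metric that counts events across the whole window is not: events before launch enter the 6-month value at full weight, and some of the same events also sit in the baseline value. By 12 months the pre-launch part has dropped out.

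The process metrics are the plan's evidence on whether measurement and treatment behaviour changed. If the 6-month values are diluted and the later ones are not, a difference between Full Support and Self-Guided could look weak at the time point the plan calls primary. It could then seem to strengthen by 12 months, even if practice changed once, at launch, and stayed there. The tests over 6, 12 and 18 months would pick up that pattern.

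**Working it through.** **Inputs from the plan:** the 12-month window; the baseline, 6-, 12- and 18-month window rules; the June 15, 2019 example; the May 15 to Aug 31 launch range. **Assumptions, not in the plan:** all events in the window are pooled, visits are evenly spread, and the effect is immediate and constant.

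**1. Reproduce the plan's figure.** Baseline ends in month 5 (May) and the 6-month window in month 12 (December): 12 − 5 = 7 months offset, as stated.

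**2. Pre-launch content of the example.** Jan 1 to June 14 is 31 + 28 + 31 + 30 + 31 + 14 = 165 days, and 165/365 = 45.2%. Jan 1 to May 31 is 151 days (151/365 = 41.4%) and also lies in the baseline window. The 12-month window (July 1, 2019 to June 30, 2020) and the 18-month window (calendar 2020) hold 0 pre-launch days.

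**3. Share of a constant effect that is read.** Baseline holds no post-launch time, so share read = 1 − pre-launch share. Apparent growth from 6 to 12 months = 1 / share read.

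| Launch (2019) | 6-month window | Pre-launch | Effect read | Growth |
|---|---|---|---|---|
| May 15 | Dec 1, 2018–Nov 30, 2019 | 165/365 = 45.2% | 54.8% | 1.83 |
| June 2 | Jan 1–Dec 31, 2019 | 152/365 = 41.6% | 58.4% | 1.71 |
| June 15 | Jan 1–Dec 31, 2019 | 165/365 = 45.2% | 54.8% | 1.83 |
| June 30 | Jan 1–Dec 31, 2019 | 180/365 = 49.3% | 50.7% | 1.97 |
| July 2 | Feb 1, 2019–Jan 31, 2020 | 151/365 = 41.4% | 58.6% | 1.71 |
| Aug 31 | Mar 1, 2019–Feb 29, 2020 | 183/366 = 50.0% | 50.0% | 2.00 |

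Over every launch day from May 15 to Aug 31 the pre-launch share is 41–50%, mean 46%. This holds whether or not a launch on the 1st makes that month the first full month. The effect read is therefore 50–59%, and apparent growth is 1.7–2.0 times.

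**4. Monthly series in the example.** Post-launch days in the windows ending at months 1 to 6 are 47, 78, 108, 139, 169 and 200 of 365: 13, 21, 30, 38, 46 and 55%. Their mean is 741/6/365 = 34%. A month 1–6 model of these metrics would show a steady rise from a constant effect, and its average would be about one third of that effect.

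**5. Sensitivity of the 45% in the example.**
- If post-launch visit volume is r times pre-launch volume, the share is 165/(165 + 200r): 48% at r = 0.9 and 40% at r = 1.25.
- Eligibility needs a hypertension encounter in the first six months of the window, which is mostly pre-launch. With Poisson visits at λ per year, h = λ/2 and f = h/(1 − e^(−h)), the share is f × (165/181)/(f + h): 56% at λ = 2 and 46% at λ = 8.

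**6. Counting only the six full months after launch.** In the example this is July 1 to Dec 31, 2019 (184 days). Pre-launch share is 0%, the effect read is 100%, and the 12-to-6-month ratio is 1.0. On sampling noise, treat each day as one independent visit unit. In the pooled change the 151 shared days cancel, leaving 214 days on each side, 200 of them post-launch on the later side. Signal to noise per unit effect is 200/√(2 × 214) = 9.7. For 184 against 184 days it is √(184/2) = 9.6. The shorter window loses almost nothing on this count.

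**The case against.** The strongest reply is that pooling is never stated. The opening rule goes on to allow criteria based on the most recent value, Metric 3 has its own 3-month period, and query construction is left to supplemental materials that are not among the documents reviewed. This stands in part. Pooling is the natural reading of Metrics 4, 5 and 7, and for Metric 8 a less certain one, but it remains an inference. The figures are conditional on it.

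Metric 6 cannot be given the calendar share. It counts persons, so its dilution depends on which uncontrolled visit is the index. That stands.

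A reader might infer that any growth between 6 and 12 months is made by the window. The documents do not support that. Interventions describes facilitation over 6 months with incremental changes, so a real effect may build up. What remains is that the pooled values cannot separate real growth from the mechanical part.

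A reader might also infer that the window favours one randomized arm. It does not: both arms follow the same rule, and dilution cannot create a difference where none exists. The secondary-outcome and time-pattern analyses are exploratory, and the 12- and 18-month values are free of pre-launch time.

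The plan does disclose the window, with an example. It acknowledges the 6- versus 7-month offset, however, and says nothing about the pre-launch content or what that does to event-based metrics.

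Finally, replacing the pooled definition at every time point would create trouble. Matching months would give each time point its own baseline. In the example, the 12-month comparison period (Jan–June 2019) would contain post-launch days. Usual Care data arrive quarterly from the companion registry and would need new windows too. This stands, and it is why the change below is an addition and not a replacement.

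**Conclusion.** The point holds for Metrics 4, 5 and 7, and for Metric 8 on its natural reading. Between 41% and 50% of the 6-month window precedes launch (mean 46%; 45% in the plan's example), against none of the 12- and 18-month windows. With pooled, evenly spread visits and an immediate, constant effect, 50–59% of the effect is read at 6 months, and apparent growth by 12 months is 1.7–2.0 times. Exact halving and doubling are the extreme of this range, not its centre.

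The consequence is attenuation at 6 months and a distorted time pattern in exploratory analyses. It is not bias between the randomized arms. Nor do these figures carry over to the primary outcome, which rests on the most recent encounter and does not pool visits.

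**What to change.** State the numerator and denominator windows for Metrics 4 to 8, and which uncontrolled visit is the index for Metric 6.

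For Metrics 4, 5, 7 and 8, and for Metric 6 once its index visit is stated:

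- Keep the 12-month period for patient eligibility.
- Add, for Arm 1 versus Arm 2, a 6-month version that counts index visits only in the six full months after launch, against the same calendar months one year earlier (in the example, July–Dec 2019 against July–Dec 2018).
- Let the follow-up visit for Metrics 6 and 7 fall after the window closes, in both periods. Otherwise the share of Metric 6 index visits with a truncated 4 weeks roughly doubles, from 4/52 (8%) to 4/26 (15%).
- Base statements about 6-month uptake on this version.

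Where the tests across 6, 12 and 18 months, or any month 1–6 model of these metrics, use the pooled values, do not interpret them as growth in effect. State the dilution beside the results.

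The cost is SAP wording, a date filter, one extra look-back query, and a later run date for the metrics that need a follow-up visit. Each clinic value rests on fewer visits, although the noise check above suggests little loss relative to the undiluted effect. The Usual Care comparison can stay on the pooled definition.

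### Metric 4 counts a first reading as high only above 140/90, but control means below 140/90, so first readings of exactly 140 or 90 drop out of the repeat-measurement metric

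*Combined protocol and SAP*

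**What the plan says.** All the relevant text is in the combined protocol and SAP, Methods, under Outcomes and measurements.

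- **Metric 1 (primary outcome).** A patient is controlled "with SBP <140 mmHg and DBP < 90 mmHg, based on measurements obtained at the most recent ambulatory clinical encounter", and the values used are chosen by "using the lowest measures of SBP and DBP at that encounter". Both inequalities are strict, so a value exactly on either limit is not controlled.
- **Metric 3 (improvement).** It also sets adequate systolic control strictly below 140 mmHg.
- **Metric 4 (confirmatory repeat).** It measures whether a second reading is taken at the same visit after a high first one, with high given as "SBP>140 mmHg or DBP>90 mmHg". These inequalities are strict in the other direction.
- **Metric 5 (medication intensification).** "This process measure captures the proportion of visits where BP is uncontrolled"; it gives no cut-off of its own. Metric 6 also refers to uncontrolled hypertension without one.
- **Metric 8 (terminal digit zero).** "Inappropriate rounding of blood pressure measurements (usually to zero) leads to measurement error". A share of zeros above 10% (automated device) or above 20% (manual device) is taken as a sign of it.

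The section places the technical detail of the queries in supplemental materials, which are not part of the document.

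**The concern.** One would expect the trigger for a confirmatory repeat to be the complement of the control definition: if a reading is not in the controlled range, it calls for a repeat. As printed, the two leave a strip between them. A first reading in that strip fails the control thresholds, yet a clinic gets no credit in Metric 4 for repeating it and loses none for not repeating it.

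Two features make the strip more than a technicality. It lies on 140 and 90, both ending in zero, where the plan itself expects rounded readings to collect. It also holds the readings for which a repeat matters most to Metric 1: after a first reading of 140/80, a second systolic value only 1 mmHg lower turns the encounter from uncontrolled to controlled. Metric 4 cannot see that repeat.

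At stake is the meaning of one secondary process measure that is compared between arms as a change from baseline. The exploratory mediation analysis is also affected if Metric 4 is the variable standing for measurement accuracy there, which the plan does not say.

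**Working it through.** **Step 1: the logic, which needs no assumption.** Not controlled means SBP >=140 or DBP >=90. High under Metric 4 means SBP >140 or DBP >90. Readings that are the first but not the second have SBP = 140 with DBP <=90, or DBP = 90 with SBP <=140.

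| First reading | Within control limits? | High under Metric 4? |
|---|---|---|
| 139/89 | yes | no |
| 140/80 | no | no (gap) |
| 130/90 | no | no (gap) |
| 140/90 | no | no (gap) |
| 141/80 | no | yes |
| 140/95 | no | yes, through DBP |
| 150/90 | no | yes, through SBP |

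On the integer grid SBP 80-220, DBP 40-130, the gap holds 51 pairs with SBP = 140 (DBP 40-90) plus 61 pairs with DBP = 90 (SBP 80-140), less the shared pair 140/90: 51 + 61 - 1 = 111. With >= in Metric 4 the count is 0.

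**Step 2: how many readings this could be.** The plan gives no figure to reproduce and no distribution of readings, so everything here is assumed: SBP mean 134 or 138 mmHg (SD 17-18), DBP mean 79 (SD 11), correlation 0.5. Readings are recorded as integers, with 0%, 15% or 30% of them rounded instead to the nearest 10. The share of systolic zeros is then about 0.10 + 0.90 x f, where f is the rounded fraction: 10%, 24% and 37%.

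Let A be the share of first readings with SBP >=140 or DBP >=90, and B the share with SBP >140 or DBP >90. The gap as a share of uncontrolled-range first readings is g = (A - B)/A.

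| SBP mean | Systolic zeros | A (>=) | B (>) | g |
|---|---|---|---|---|
| 134 | 10% | 42.8% | 40.0% | 2.8/42.8 = 6.5% |
| 134 | 24% | 44.7% | 38.3% | 6.4/44.7 = 14.3% |
| 134 | 37% | 46.7% | 36.6% | 10.1/46.7 = 21.6% |
| 138 | 10% | 50.6% | 48.0% | 2.6/50.6 = 5.1% |
| 138 | 24% | 52.4% | 46.3% | 6.1/52.4 = 11.6% |
| 138 | 37% | 54.2% | 44.6% | 9.6/54.2 = 17.7% |

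So g is about 5-7%, 12-14% and 18-22%. A second set of assumptions (SBP mean 132-138, SD 16-18; DBP SD 10.5) gives 5-8%, 10-14% and 19-27% at 10%, 20% and 40% zeros, which is the same picture.

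**Step 3: what that does to Metric 4.** Metric 4 is a percentage repeated. Including the gap readings changes its level by g x (repeat rate in the gap - repeat rate among readings above the cut-off). The documents give neither rate. If they differed by 20 percentage points (an assumption), the level would move by 0.12 x 20 = 2.4 to 0.14 x 20 = 2.8 points in the middle case, and by between 0.05 x 20 = 1.0 and 0.22 x 20 = 4.4 points over the whole range. If the rates were equal, it would not move.

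**Step 4: does >= remove sensitivity to rounding?** Read columns A and B downwards. At mean 134, the Metric 4 denominator as written falls from 40.0% to 36.6% (3.4 points) as zeros rise from 10% to 37%. With >= it rises from 42.8% to 46.7% (3.9 points). At mean 138 it falls by 3.4 points as written (48.0% to 44.6%) and rises by 3.6 with >= (50.6% to 54.2%). Under >, true systolic values of 141-144 rounded to 140 leave the denominator. Under >=, true values of 135-139 rounded to 140 enter it. The direction changes and the size does not shrink.

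**The case against.** The strongest reply is that the two metrics need not be complements. Metric 1 classifies a patient by the lowest values at the most recent encounter; Metric 4 looks at the first reading of a visit. A first reading of 140/80 repeated at 136/78 is controlled under Metric 1, so the omitted readings are not the same thing as uncontrolled patients. That is right, and it is why the point is put in terms of uncontrolled-range first readings. It does not close the gap: a single 140/80 that is never repeated is uncontrolled under Metric 1 and invisible to Metric 4.

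Next, the same cut-off applies in every arm and at every time point, and the analysis compares within-clinic changes. A constant offset in Metric 4 therefore cancels, leaving only a differential change in g or in the repeat-rate difference. If g fell by 5 points more in one arm, with the 20-point difference assumed above, the effect would be 0.05 x 20 = 1 point. This stands, and it limits the importance of the point.

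Third, the printed line may be looser than the query code, which is not available here. This also stands: the finding concerns the definition as printed.

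A reader might go further and infer that, because the programme aims to improve measurement and the gap sits on rounded values, the mismatch creates a treatment-dependent drift in Metric 4 that the correction would cure. Step 4 does not support that. Any cut-off at a zero-ending value is sensitive to changes in rounding, with either operator. Nor is it true that a reading with a component at 140 or 90 is always missed: 140/95 and 150/90 qualify through the other component.

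**Conclusion.** The point holds as an inconsistency between two printed definitions, and it is minor. Metric 4 omits first readings of exactly 140 systolic or 90 diastolic when the other component is not above its limit, although the plan's own control thresholds place them in the uncontrolled range. That much is certain from the text.

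The size is not certain. The 5-7% (no digit preference) and 12-22% (24-37% systolic zeros) rest on assumed distributions and an assumed form of rounding. The effect on the Metric 4 percentage also depends on repeat rates that the documents do not give; it is probably a few points in level and less in the between-arm comparison of changes. Neither its direction nor any difference by arm can be determined from the documents.

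The consequence is confined to one of nine secondary metrics, and to the exploratory mediation analysis if Metric 4 is used there. The primary outcome and the three primary tests do not use Metric 4.

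**What to change.** In Metric 4, define a high first reading as SBP >=140 mmHg or DBP >=90 mmHg, so that it is the exact complement of the Metric 1 thresholds. Then confirm that the query specification in the supplemental materials uses the same operators. If the code already does, only the text needs correcting. If strict inequalities are intended, say so and give the reason. This changes how a metric is computed, not how patients are managed.

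It would also help to state that uncontrolled in Metrics 5 and 6 carries the Metric 1 meaning, so that one boundary serves all the process measures.

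The cost is two operators, a check of the query, and a rerun of Metric 4 for any period already extracted. Sample size and the primary analysis are unaffected. The change should not be presented as protection against rounding; the Metric 8 results should be read beside Metric 4 for that.
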